4.3. Secondary Endpoints Analyses

All pharmacokinetic analyses will be performed on the Pharmacokinetic Analysis Set. For PK endpoints, all analysis will be performed by Part i.e. Part A (Cohorts 1 and 2 combined), Part B (Cohorts 3 and 4 combined) and Part C (Cohort 5).

Derived pharmacokinetic parameters as data permit, including (but not limited to):

Part A, Cohorts 1 & 2:

- Area under the plasma GSK3923868 concentration versus time curve from time zero to last quantifiable concentration (AUC(0-t)) and from time zero to infinity (AUC(0-∞)) (if determined).
- Maximum observed GSK3923868 plasma concentration (C_{max}).
- Time to maximum observed plasma drug concentration (T_{max}).

Part B, Cohorts 3 & 4:

- AUC(0-□) on Day 1 and Day 14 ($\square=24h$ for once a day dosing regimen) (if determined).
- Cmax and Tmax on Day 1 and Day 14.

Part C, Cohort 5:

- AUC(0-□) on Day 1 and Day 7 ($\square=24h$ for once a day dosing regimen) (if determined).
- Cmax and Tmax on Day 1 and Day 7.

4.3.1. Definition of endpoint(s)

If the AUC(0- τ) or AUC(0- ∞) is not calculatable due to non-quantifiable plasma GSK3923868 data, AUC(0- t') may be calculated instead. t' is the common timepoint for all subjects for the corresponding dose or cohort.

Parameter	Parameter Description
AUC(0- t)	Area under the concentration-time curve from time zero to the time of the last quantifiable concentration ($C(t)$) will be calculated using the linear trapezoidal rule for each incremental trapezoid and the log trapezoidal rule for each decremental trapezoid.
AUC(0-□)	Area under the concentration-time curve over the dosing interval.
AUC(0- ∞)	Area under the concentration-time curve extrapolated to infinity will be calculated as follows: $AUC = AUC(0-t) + C(t)/\lambda z$.
Cmax	Maximum observed concentration, determined directly from the concentration-time data over the dosing interval.
C_{\square}	Trough concentration
Tmax	Time to reach Cmax, determined directly from the concentration-time data.
$t^{1/2}$	Apparent terminal half-life will be calculated as: $t^{1/2} = \ln 2 / \lambda z$ 
(NOTE: λz is the terminal phase rate constant).

NOTE: Additional parameters may be included as required.

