## 7.3. Participant Discontinuation/Withdrawal from the Study

- A participant may withdraw from the study at any time at his/her own request or may be withdrawn at any time at the discretion of the investigator for safety, behavioural, or compliance reasons. This is expected to be uncommon.
- At the time of discontinuing from the study, if possible, the procedures outlined in the SOA on the day of discharge from the clinical unit should be completed (i.e. Days 2, 3, 18 and 8 for Parts A Cohort 1, A Cohort 2, B and C respectively).
- The participant will be permanently discontinued both from the study intervention and from the study at that time.
- If the participant withdraws consent for disclosure of future information, the Sponsor may retain and continue to use any data collected before such a withdrawal of consent.
- If a participant withdraws from the study, he/she may request destruction of any samples taken and not tested, and the Investigator must document this in the site study records.
- If participants prematurely discontinue in the study, they may be replaced at the discretion of the Medical Monitor in consultation with the Principal Investigator.

In Part A, the replacement participant will be assigned to the same treatment sequence and may start the treatment period where the last participant prematurely discontinued. In Parts B and C participants will be assigned to same treatment as the participant prematurely discontinued.

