4.3.2.1. Dose Proportionality

The following pharmacokinetic statistical analyses will only be performed if sufficient data are available (i.e. if more than 5 subjects have well defined plasma profiles). If the dose with limited data is at the lower end of the dose range, the data will be excluded and the appropriate analysis conducted on the rest of the data. However if there are non-calculable PK parameter data at intermittent doses no statistical analyses will be performed. A minimum of 3 doses will be required to assess dose proportionality. The assessment of dose proportionality will utilise Part A data only.

Dose proportionality will be assessed using the following two methods:

Pharmacokinetic Statistical Analyses for Dose Proportionality: Power Method	
Endpoint(s)	
• AUC(0-Inf) (if determined, otherwise use AUC(0-t)), Cmax	• Each endpoint to be assessed separately.
Model Specification	
• $\log_e(Y) = \beta \times \log_e(\text{dose}) + \log_e(\alpha)$ where Y is the pharmacokinetic parameter and $\log_e(\alpha)$ is an intercept term.	
Model Results Presentation	
• The coefficient of the slope with 90% confidence intervals, on the log scale, will be calculated, using the pooled estimate of variance, and used to assess dose proportionality.	• Point estimates and confidence intervals for the slope will be reported to 2 decimal places

Pharmacokinetic Statistical Analyses for Dose Proportionality: ANOVA Method	
Endpoint(s)	
• AUC(0-Inf) (if determined, otherwise use AUC(0-t')), Cmax	• Each endpoint to be assessed separately.
Model Specification	
• The PK parameter will be dose-normalised prior to loge-transformation by multiplying by reference dose / dose	• Dose will be fitted as a fixed effect, subject as a random effect using DDFM=KR.
• Separate lines will be fitted for each cohort by including terms for cohort and cohort*log _e (dose). If the slopes are not significantly (p-value<0.05) different from each other, the interaction term will be removed and a single slope estimate obtained. If the slopes are significantly different from each other, a separate slope estimate and associated 90% confidence interval will be reported for each cohort.	• The reference dose will be chosen based on the lowest clinically relevant dose over which PK can be adequately described, with each other dose as the test doses in the construction of the ratio $\mu(\text{test})/\mu(\text{reference})$.
Model Results Presentation	

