• Point estimates for the adjusted means on the log _e scale, the mean difference between each dose (test) and the reference dose and associated 90% confidence interval will be constructed using the residual variance. These will not be presented.	• The point estimate and confidence interval will then be exponentially back-transformed to allow the presentation of the adjusted (least square) geometric means for each treatment

Pharmacokinetic Statistical Analyses for Dose Proportionality: ANOVA Method	
	(dose), and point estimates and associated 90% confidence intervals for the ratio test/reference.
•	Point estimates and 90% confidence intervals for AUC, Cmax will be reported to 2 decimal places. Treatment ratios and 90% CIs will be plotted by dose.
•	Plots will also be provided showing the adjusted geometric mean ratio of test to reference treatment (dose) for AUC(0-∞) or AUC(0-t'), and Cmax together with 90% confidence interval.

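### If AUC(0-∞) is not determined at every Part A dose, the dose-proportionality fallback does not use one time window across the doses, which can make linear PK look more than dose-proportional

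*SAP*

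**What the plan says.** - **Scope.** SAP 4.3 analyses Part A PK with Cohorts 1 and 2 combined.
- **Power method (SAP 4.3.2.1).** The endpoint is "AUC(0-Inf) (if determined, otherwise use AUC(0-t)), Cmax". SAP 4.3.1 ends AUC(0-t) at each profile's last quantifiable concentration.
- **ANOVA method (same section).** The fallback is printed as AUC(0-t'), and the results plots show the "ratio of test to reference treatment (dose) for AUC(0-∞) or AUC(0-t'), and Cmax". Each dose is compared with one reference dose, the lowest clinically relevant dose at which PK is adequately described.
- **Definition of t' (SAP 4.3.1; same wording in Protocol 9.4.2).** It "is the common timepoint for all subjects for the corresponding dose or cohort".
- **Cohort term.** "Separate lines will be fitted for each cohort by including terms for cohort" is printed under the ANOVA. Its reference to a single slope estimate fits the power model, and it is read that way here.
- **Safeguards.** The analysis runs only "if more than 5 subjects have well defined plasma profiles". For sparse data at low doses the SAP has a separate rule: "If the dose with limited data is at the lower end of the dose range, the data will be excluded". Nothing is analysed if parameters are non-calculable at intermediate doses, and at least three doses are needed.
- **Sampling.** Protocol Amendment 03 extended Cohort 2 PK sampling from 24 h to 48 h. The discharge days in Protocol 7.3 agree: "Days 2, 3, 18 and 8 for Parts A Cohort 1, A Cohort 2, B and C respectively".

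No visible passage sets one window across the doses compared. Nor does any say whether AUC(0-∞) being determined is judged per profile, per dose or per analysis.

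**The concern.** A dose-proportionality comparison needs the same measure of exposure at every dose. Under linear PK a higher dose stays quantifiable at least as long as a lower one, and Cohort 2, which holds the three highest doses, is also sampled for longer. A fallback window tied to the last quantifiable sample, to the dose or to the cohort therefore tends to lengthen as the dose rises. More of the true AUC is then captured at high doses than at low ones, and assay sensitivity or sampling length can be reported as more than dose-proportional exposure.

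The stakes are limited. The SAP tests no hypothesis and states no proportionality limit. Cmax does not depend on the window, and escalation uses Cmax and AUC up to 24 h (Protocol 4.3.1). What is at risk is the descriptive statement on linearity and whatever later dose selection draws on it.

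**Working it through.** The documents give no figure for bias or precision of this analysis, so there is none to reproduce.

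**1. True value.** Predicted AUC in Protocol Table 4 is linear: 11.4 / 0.19 = 60 and 3000 / 50 = 60. The true slope is ln 60 / ln 60 = 1.00, and every true dose-normalised ratio is 1.00.

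**2. What each reading of the fallback does under linear PK**

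| Fallback | Slope | Cross-cohort ANOVA ratio |
|---|---|---|
| AUC(0-t) | tends above 1 | distorted |
| t' per dose | tends above 1 | distorted |
| t' per cohort, no cohort term | tends above 1 | distorted |
| t' per cohort, cohort term in the power model | 1.00 | distorted |
| one t' for all doses | 1.00 | 1.00 |

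The sign of the ratio distortion depends on the reference. It is above 1 for Cohort 2 test doses if the reference is a Cohort 1 dose, and below 1 for Cohort 1 test doses if the reference is a Cohort 2 dose. Either way it reads as more than proportional.

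**3. Sampling length alone.** Assume mono-exponential decline with half-life h and every sample quantifiable. The share of AUC beyond 24 h is x = 2^(-24/h), and beyond 48 h it is x². The ratio of windows is (1 - x²)/(1 - x) = 1 + x.

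| h (assumed) | x | AUC(0-48)/AUC(0-24) |
|---|---|---|
| 6 h | 0.0625 | 1.06 |
| 8 h | 0.125 | 1.13 |
| 12 h | 0.25 | 1.25 |
| 24 h | 0.50 | 1.50 |

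The documents give no acceptance limit for AUC(0-∞). If at most 20% may be extrapolated (assumed), Cohort 1 fails only when x > 0.20, that is h > 24 × ln 2 / ln 5 = 10.3 h. At 6 h and 8 h AUC(0-∞) would be accepted and no fallback would arise.

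At h = 12 h the step between cohorts is ln 1.25 = 0.223. Over the six log doses, the deviations from the mean have sum of squares 11.31, and the three Cohort 2 deviations sum to 3.55. A single line therefore gains 0.223 × 3.55 / 11.31 = 0.07, a slope of 1.07. With a cohort term the step is absorbed and the slope is 1.00, but a Cohort 2 to Cohort 1 ratio is still 1.25 (0.80 if the reference is a Cohort 2 dose).

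**4. Kinetics anchored on the protocol.** Protocol 4.3 predicts clearance 37 L/h and volume 51 L, so mean residence time is 51 / 37 = 1.38 h. Noise-free bi-exponential profiles were matched to this (half-life 1.2 to 2.2 h), scaled to Table 4, and cut at an assumed assay limit of 0.002 to 0.02 ng/mL (12 cases). With at least three post-peak points and the 20% limit (both assumed), AUC(0-∞) is determined at every retained dose in 12 of 12. Had the fallback been used anyway, the AUC(0-t) slope over 250 to 3000 mcg would be 1.00 to 1.03, and the 500:250 ratio with a per-cohort t' 1.00 to 1.05.

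**5. Assumed long half-life.** Here the half-life is 4 to 16 h, the terminal phase 30 to 70% of AUC, and the assay limits are the same (36 cases). A dose is kept if quantifiable to at least 4 h (assumed). The fallback is triggered in 8 of 36 cases if the model starts at 250 mcg, and in 14 of 36 if every dose passing the 4 h cut is kept. In triggered cases the AUC(0-t) slope is about 1.06 to 1.21. With one t' common to all doses it is 1.00.

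**The case against.** The strongest reply is that AUC(0-∞) comes first and the fallback may never be used. That stands, and it governs the size. A reader might infer that the plan will generally overstate the slope. For example, a simulation that applies the fallback in all 36 long-half-life cases (assumed between-subject CV 30%) gives a median AUC(0-t) slope of 1.04 and a 90% CI wholly above 1 in a median 37% of trials, against 4% with one common t'. Those figures average over many cases in which AUC(0-∞) would be determined, so they are not expected effects of this plan. The amendment lengthened Cohort 2 sampling for a better terminal half-life estimate. That hints at a longer tail than step 4 assumes, but it does not say 24 h was inadequate for AUC, and it makes AUC(0-∞) more attainable in Cohort 2.

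A reader might also infer that the two methods deliberately use different AUCs. The power method's AUC(0-t) may be a lost prime: other symbols in these parameter names are damaged, and the plots list only AUC(0-∞) and AUC(0-t'). The AUC(0-t) figures would then not apply. The gap remains, because t' is still common only within a dose or cohort.

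Nor do the documents support saying that cross-cohort ratios always exceed 1, since that depends on the reference dose. Even the slope direction is a tendency: losing low-exposure profiles at low doses pulls it down.

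Excluding limited-data low doses reduces the effect, but the triggered cases in step 5 remain after a comparable cut. The Output and Programming Specification, which is not available, may fix one t'. If so, the SAP need only say so.

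**Conclusion.** The point holds as a conditional one. When AUC(0-∞) is not determined at every Part A dose in the model, the stated fallback does not give the doses a common window, and under linear PK it tends to make exposure look more than dose-proportional. With a per-cohort t' and the cohort term in the power model, the slope is not biased and only the cross-cohort ANOVA ratios are.

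The documents do not fix the size. It is negligible with the protocol's predicted clearance and volume, and a slope of roughly 1.06 to 1.21 with AUC(0-t) in the assumed long-half-life cases that trigger the fallback. Those figures rest on assumed assay limits, half-lives, terminal shares, a 4 h cut and a 20% extrapolation limit, without noise. Because the analysis is secondary and descriptive, and Cmax and dose escalation are unaffected, this is a minor but real correction.

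**What to change.** In SAP 4.3.1 and 4.3.2.1:

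- Name the same AUC in the power and ANOVA methods.
- If AUC(0-∞) is not determined at every dose in the model, use AUC(0-t') for all doses, with one t' common to all doses analysed and no later than 24 h when both cohorts are included.
- Set t' after the existing exclusion of low doses with limited data.
- Do not mix AUC types within a model.
- Keep AUC(0-t) as a descriptive parameter, and report the share of top-dose AUC that t' covers.

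The cost is SAP wording only, with parameters already defined. The downside is that a common t' leaves out part of the high-dose tail and would not show late-phase non-linearity. In the long-half-life simulation it covered 51 to 89% of the 3000 mcg AUC(0-t) (median 76% at CV 30%, 72% at CV 50%), and 92 to 94% for the protocol-anchored profiles. It also does not remove the loss of low-exposure profiles: the lowest mean slope with one t' was 0.96. Reporting the covered share makes the first limit visible.

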4.3.2. Main analytical approach

Plasma GSK3923868 concentration-time data will be analysed by non-compartmental methods with WinNonlin. Calculations will be based on the actual sampling times recorded during the study.

Pharmacokinetic data will be presented in graphical form and will be summarised descriptively. Analysis of dose proportionality (Part A), steady state assessment and dose accumulation (Parts B and C) will be conducted.

4.3.2.1. Dose Proportionality

The following pharmacokinetic statistical analyses will only be performed if sufficient data are available (i.e. if more than 5 subjects have well defined plasma profiles). If the dose with limited data is at the lower end of the dose range, the data will be excluded and the appropriate analysis conducted on the rest of the data. However if there are non-calculable PK parameter data at intermittent doses no statistical analyses will be performed. A minimum of 3 doses will be required to assess dose proportionality. The assessment of dose proportionality will utilise Part A data only.

Dose proportionality will be assessed using the following two methods:

Pharmacokinetic Statistical Analyses for Dose Proportionality: Power Method	
Endpoint(s)	
• AUC(0-Inf) (if determined, otherwise use AUC(0-t)), Cmax	• Each endpoint to be assessed separately.
Model Specification	
• $\log_e(Y) = \beta \times \log_e(\text{dose}) + \log_e(\alpha)$ where Y is the pharmacokinetic parameter and $\log_e(\alpha)$ is an intercept term.	
Model Results Presentation	
• The coefficient of the slope with 90% confidence intervals, on the log scale, will be calculated, using the pooled estimate of variance, and used to assess dose proportionality.	• Point estimates and confidence intervals for the slope will be reported to 2 decimal places

Pharmacokinetic Statistical Analyses for Dose Proportionality: ANOVA Method	
Endpoint(s)	
• AUC(0-Inf) (if determined, otherwise use AUC(0-t')), Cmax	• Each endpoint to be assessed separately.
Model Specification	
• The PK parameter will be dose-normalised prior to loge-transformation by multiplying by reference dose / dose	• Dose will be fitted as a fixed effect, subject as a random effect using DDFM=KR.
• Separate lines will be fitted for each cohort by including terms for cohort and cohort*log _e (dose). If the slopes are not significantly (p-value<0.05) different from each other, the interaction term will be removed and a single slope estimate obtained. If the slopes are significantly different from each other, a separate slope estimate and associated 90% confidence interval will be reported for each cohort.	• The reference dose will be chosen based on the lowest clinically relevant dose over which PK can be adequately described, with each other dose as the test doses in the construction of the ratio $\mu(\text{test})/\mu(\text{reference})$.
Model Results Presentation	
• Point estimates for the adjusted means on the log _e scale, the mean difference between each dose (test) and the reference dose and associated 90% confidence interval will be constructed using the residual variance. These will not be presented.	• The point estimate and confidence interval will then be exponentially back-transformed to allow the presentation of the adjusted (least square) geometric means for each treatment

Pharmacokinetic Statistical Analyses for Dose Proportionality: ANOVA Method	
	(dose), and point estimates and associated 90% confidence intervals for the ratio test/reference.
•	Point estimates and 90% confidence intervals for AUC, Cmax will be reported to 2 decimal places. Treatment ratios and 90% CIs will be plotted by dose.
•	Plots will also be provided showing the adjusted geometric mean ratio of test to reference treatment (dose) for AUC(0-∞) or AUC(0-t'), and Cmax together with 90% confidence interval.

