4.1.4. Model Checking Diagnostics

Model checking diagnostics for dose proportionality and dose accumulation analysis will include the following:

- The Kenward and Roger method for approximating the denominator degrees of freedom and correcting for bias in the estimated variance-covariance of the fixed effects will be used.
- An unstructured covariance structure for the R matrix will be used by specifying 'type=UN' on the REPEATED line.
 - In the event that this model fails to converge, alternative correlation structures may be considered such as CSH or CS.
 - Akaike's Information Criteria (AIC) will be used to assist with the selection of covariance structure.
- Distributional assumptions underlying the model used for analysis will be examined by obtaining a normal probability plot of the residuals and a plot of the residuals versus the fitted values (i.e. checking the normality assumption and constant variance assumption of the model respectively) to gain confidence that the model assumptions are reasonable.

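### The cohort slope check for dose proportionality sits in the ANOVA method, where it has 0 degrees of freedom; it belongs in the Power model, with one stated covariance structure

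*SAP*

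**What the plan says.** SAP 4.3.2.1 gives two methods, both using Part A data only.

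- **Power method.** log_e(Y) is regressed on log_e(dose), and one slope is reported with a 90% CI. The equation has no cohort, interaction or subject term.
- **ANOVA method.** The parameter is dose-normalised and log-transformed. "Dose will be fitted as a fixed effect, subject as a random effect using DDFM=KR". The results call for "presentation of the adjusted (least square) geometric means for each treatment" and for test/reference ratios with 90% CIs. No slope appears among these results.

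The cohort rule is a bullet within the ANOVA model specification: "Separate lines will be fitted for each cohort by including terms for cohort and" cohort × log_e(dose). If the slopes do not differ at p<0.05, "the interaction term will be removed and a single slope estimate obtained"; otherwise one slope per cohort is reported, each with a 90% CI.

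Three other statements bear on this:

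- SAP 4.3: "all analysis will be performed by Part i.e. Part A (Cohorts 1 and 2 combined".
- SAP 4.3.2.1, on sparse data: "If the dose with limited data is at the lower end of the dose range, the data will be excluded". At least three doses must remain.
- SAP 4.1.4, for dose proportionality and accumulation: "An unstructured covariance structure for the R matrix will be used by specifying" (the UN option follows). Simpler structures enter only if that fit breaks down: "In the event that this model fails to converge, alternative correlation structures may be considered such as CSH or CS".

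**The concern.** A mean per dose requires categorical dose. Once every dose has its own mean, and each dose is given in one cohort only, nothing is left for a cohort term or a cohort-specific slope to explain. The rule that decides between one slope and two then cannot be run in the model where it is written. Because Part A is analysed with the cohorts combined, this is the only stated rule for deciding whether one slope serves both. If it fails in programming, someone must choose an alternative that the SAP does not describe.

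The within-subject structure is unsettled too. Each participant contributes two or three active profiles. The ANOVA box names a random subject effect, SAP 4.1.4 names an unstructured R matrix, and the Power equation shows neither.

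**Working it through.** **Inputs.** Doses by cohort: Protocol 6.1. Four sequences of three participants per cohort: Protocol 4.1 Table 2 and SAP 1.2. One cohort per participant: Protocol 4.1. Model terms: SAP 4.3.2.1 and 4.1.4.

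**1. The plan's own figure.** In each period one sequence of three is on placebo, so 12 − 3 = 9 are on active, as SAP 5 states. Its probabilities reproduce: 0.95^9 = 63.0% and 0.80^9 = 13.4%. Six doses × 9 = 54 active records from 24 participants. The SAP gives no df for the slope check.

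**2. Rank of the ANOVA model.** Let D_j indicate dose j. At the planned doses,

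- cohort 1 indicator = D_50 + D_100 + D_250;
- cohort 1 × log(dose) = log(50)·D_50 + log(100)·D_100 + log(250)·D_250;

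and likewise for Cohort 2 with 500, 1000 and 3000. Every added column is a combination of dose columns. A default LS mean here takes equal cohort weights and mean log dose.

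| Fixed effects | Rank | Default LS means estimable | Default ratios to 50 mcg estimable |
|---|---|---|---|
| dose | 6 | 6/6 | 5/5 |
| dose + cohort | 6 | 0/6 | 2/5 |
| dose + cohort + cohort × log(dose) | 6 | 0/6 | 0/5 |

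The interaction test has 6 − 6 = 0 df. Slope 1, slope 2 and their difference are all non-estimable. Dose plus a single log(dose) term also has rank 6, so a common slope is not estimable either. Dropping only the interaction, as the rule directs, leads to the second row and does not restore the default LS means. If the means are taken at each dose's own cohort and own log dose, all three models give 6/6 means and 5/5 ratios.

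**3. If doses are modified.** With one dose level common to both cohorts the ranks are 5, 6, 6, and the slope test still has 0 df. With two common levels they are 4, 5, 6, and it has 1 df.

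**4. The same check in the Power model.** Columns: intercept and log(dose), then cohort, then cohort × log(dose).

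| Doses kept | Ranks | Interaction df |
|---|---|---|
| all six | 2, 3, 4 | 1 |
| without 50 | 2, 3, 4 | 1 |
| without 50 and 100 | 2, 3, 3 | 0 |

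In the last row four doses remain, so the SAP minimum of three is met, but Cohort 1 keeps one dose and has no slope of its own.

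**5. The bullet read as a separate regression.** log(Y × ref/dose) = log(Y) + log(ref) − log(dose), so each slope falls by exactly 1 and the difference is unchanged. On one simulated data set (mixed model, random subject), the log(Y) slopes were 1.0519 and 0.8526, and the dose-normalised slopes 0.0519 and −0.1474. Both scales gave a difference of −0.1993, z = −2.0657 and p = 0.0389.

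**6. Covariance.** Indexed by dose, an unstructured matrix has 6 × 7/2 = 21 parameters, of which 15 are covariances. Each of the 6 within-cohort dose pairs is observed together in 6 participants; each of the 9 cross-cohort pairs in none. Indexed by period within cohort and common to both cohorts, it has 3 × 4/2 = 6 parameters, and each covariance rests on 6 + 6 = 12 participants.

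**The case against.** Lines and slopes make sense only with continuous log(dose), so a statistician could read the bullet as a separate regression, and the check then works with 1 df. That stands as a possible reading, but the SAP does not state it. It would also put slopes of β − 1 (proportionality at 0) beside the Power slope (proportionality at 1), without a label.

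The loss of LS means depends on software defaults, and the means and ratios can be recovered. This is correct, but the SAP specifies neither the weights nor the contrasts that would do it.

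The dose-normalised ratios plotted by dose, and the residual plots in SAP 4.1.4, would also show departures from proportionality. They are useful, but neither is a rule for choosing one slope or two.

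SAP 4.1.4 covers dose proportionality generally, so it reaches the Power model, and a random subject effect amounts to compound symmetry, which it lists as a fallback. However, that fallback is tied to non-convergence, whereas the ANOVA box adopts random subject outright. Using both is redundant, because an unstructured matrix absorbs the subject variance.

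The strongest point is consequence. No hypothesis is tested, and the dose-escalation limits in Protocol 6.5.1 do not use this check. The check is also weak: assuming within- and between-subject CVs of 20–40% (the documents give none), its power for a slope difference of 0.2 is about 23–65%. This limits the severity but does not make the rule executable where it stands.

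**Conclusion.** Wrong as written, and it should be fixed. At the planned doses the cohort slope rule has 0 df in the ANOVA with categorical dose, and neither cohort slopes nor a single slope can be estimated there. In the Power model it has 1 df, provided each cohort keeps at least two doses. Separately, SAP 4.1.4 and the ANOVA box name different within-subject structures.

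The result rests on dose being categorical, which the promised mean per dose requires, and on the planned doses not overlapping between cohorts; overlap at one level would not rescue the test. The non-estimable LS means are a result under default settings only.

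The impact is limited. This is a descriptive secondary PK analysis, the pooled Power slope is unaffected, the dose ratios are recoverable, and a run on dummy data would expose the rank failure before unblinding.

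**What to change.** 1. **ANOVA method:** delete the bullet on cohort and cohort × log_e(dose). Keep dose as a categorical fixed effect.
2. **Power method:** add the slope check (cohort and cohort × log_e(dose)) on the un-normalised log parameter. Run it only if each cohort retains at least two doses after any low-dose exclusion. Say in advance whether the cohort main effect stays once the interaction is dropped.
3. **Within-subject term:** write it into the Power model and reconcile it with SAP 4.1.4. Either state that a random subject effect with Kenward–Roger df (compound symmetry) replaces the unstructured R matrix for dose proportionality, or keep the unstructured matrix, index it by period within cohort and drop the random subject effect. Make the same choice in both methods.

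The cost is SAP wording only; no design or data-collection change is needed.
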